3.1 Inclusion Criteria

Participants must meet the following criteria on screening examination to be eligible to participate in the study:

1. Prior diagnosis of Langerhans Cell Histiocytosis (stratum 1) or LCH-related disorder (stratum 2) established by standard diagnostic criteria and confirmed histologically.
2. Evidence of active disease (histological confirmation of reactivation or progression is not required).
3. Performance Score > 70% (use Lansky score for age <16 and Karnofsky score for age ≥16, see Appendix I).
4. Patients of all ages will be eligible.
5. Provide signed written informed consent.

CONFIDENTIAL

This document is confidential. Do not disclose or use except as authorized.

6. In stratum 1, patients must have failed one prior systemic chemotherapy regimen. In stratum 2, RDD patients must have failed treatment with corticosteroid. EDC patients who have confirmed BRAF V600E mutations must have failed treatment with BRAF inhibitor or are not considered to be eligible for such treatment.
7. There is no limitation of amount or the type of prior therapy or drugs.
8. Female patients of childbearing potential must have a negative serum pregnancy test within 14 days prior to enrollment. Male and female patients must use an effective contraceptive method during the study and for a minimum of 6 months after study treatment.
9. Capable of understanding the investigational nature, potential risks and benefits of the study, and able to provide valid informed consent.
10. Participants must have adequate marrow functions as defined below, except those who involvement of hematopoietic system for whom these criteria can be waived:
 - Absolute neutrophil count ≥ 750 cells/ μ L
 - Platelets ≥ 750 cells/ μ L
11. Participants must have adequate organ function as defined below:
 - Total bilirubin ≤ 2.5 x institutional upper limit of normal.
 - AST (SGOT)/ALT (SGPT) < 2.5 x institutional upper limit of normal unless it is related to involvement by LCH.
 - Pediatric Population (patients < 18 years): Creatinine within normal limits or calculated creatine clearance ≥ 90 mL/min/1.73 m² as calculated by the Schwartz formula for estimated glomerular filtration rate (GFR) where GFR (mL/min/1.73 m²) = k x Height (cm)/serum creatinine (mg/dL). k is proportionally constant which varies with age and is a function of urinary creatine excretion per unit of body size; 0.45 up to 12 months of age; 0.55 children and adolescent girls; and 0.70 adolescent boys.

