9.1 Definition of Response Criteria

Table 4: Three Categories of Response

Response Category	Definition
Better	
 Complete disease resolution (NAD) Regression (AD better)
Intermediate	
 Stable (unchanged)
Worse	
 Progression*

* Progression of skeletal lesions is defined as unequivocal enlargement of the size of existing lesions and/or appearance of new lesions. In patients with risk organ involvement the overall response (and hence therapeutic decision) depends on response in risk organs.

9.2 CRITERIA FOR RESPONSE – STRATUM 2

For PET-based assessments, a clinical response of progressive metabolic disease (PMD), no metabolic response (NMR), partial metabolic response (PMR), or complete metabolic response (CMR) will be determined. PMD/PD includes radiological evidence of progression per Lugano Classification Revised Staging System for malignant lymphoma⁶⁹. The PET scan metabolic uptake will be graded using the Deauville 5-point scale, with a score of ≤ 3 considered to represent a CMR.

Deauville 5-point scale: 1 = no uptake above background; 2 = uptake \leq mediastinum; 3 = uptake $>$ mediastinum but \leq liver; 4 = uptake moderately $>$ liver; 5 = uptake markedly higher than liver and/or new lesions; X = new areas of uptake unlikely to be related to lymphoma.

CONFIDENTIAL

This document is confidential. Do not disclose or use except as authorized.

Table 5: CMR / CR

Response/Site	FDG PET-CT-Based (Complete Metabolic Response)	CT-Based (CR) ^a All of the following:
Lymph nodes and extralymphatic sites	Score 1, 2 or 3 with or without a residual mass on 5-Point-Scale. It is recognized that in Waldeyer's ring or extranodal sites with high physiologic uptake or with activation within spleen or marrow (eg, with chemotherapy or myeloid colony-stimulating factors), uptake may be greater than normal mediastinum and/or liver. In this circumstance, complete metabolic response may be inferred if uptake at sites of initial involvement is no greater than surrounding normal tissue even if the tissue has high physiologic uptake.	Target nodes/nodal masses must regress to ≤ 1.5 cm in LDi No extra lymphatic sites of disease
Non-measured lesion	Not applicable	Absent
Organ enlargement	Not applicable	Regress to normal
New lesions	None	None
Bone marrow ^b	No evidence of FDG-avid disease in marrow	Normal by morphology; if indeterminate, IHC negative

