^a CT-Based could also apply to MRI-based

^b Only if bone marrow involvement at diagnosis

Table 6: PMR / PR

Response/Site	FDG PET-CT-Based (Complete Metabolic Response)	CT-Based (CR) ^a All of the following:
Target nodes/nodal masses, extranodal lesions	Score 4 or 5 with reduced uptake compared with baseline and residual mass(es) of any size At interim, these findings suggest responding disease At end of treatment, these findings suggest residual disease	≥ 50% decrease in SPD of up to 6 target measurable nodes and extranodal sites When a lesion is too small to measure on CT, assign 5mm X 5mm as the default value; when no longer visible, 0 X 0mm; for a node > 5mm X 5mm, but smaller than normal, use actual measurement for calculation
Non-measured lesion	Not applicable	Absent/normal, regressed, but no increase
Organ enlargement	Not applicable	Spleen must have regressed by >50% in length beyond normal
New lesions	None	None
Bone marrow ^b	Residual uptake higher than uptake in normal marrow but reduced compared with baseline (diffuse uptake compatible with reactive changes from chemotherapy allowed). If there are persistent focal changes in the marrow in the context of a nodal response, consideration should be given to further evaluation with MRI or biopsy or an interval scan.	Not applicable

^a CT-Based could also apply to MRI-based

^b Only if bone marrow involvement at diagnosis

Table 7: NMR/ SD

Response/Site	FDG PET-CT-Based (Complete Metabolic Response)	CT-Based (CR) ^a All of the following:
Lymph nodes and extralymphatic sites	Score 4 or 5 with no significant change in FDG uptake from baseline at interim or end of treatment	< 50% decrease in SPD of up to 6 target measurable nodes and extranodal sites; no criteria for Progressive Disease met
Non-measured lesion	Not applicable	No increase consistent with Progression
Organ enlargement	Not applicable	No increase consistent with Progression
New lesions	None	None
Bone marrow ^b	No change from baseline	Not applicable

^a CT-Based could also apply to MRI-based

^b Only if bone marrow involvement at diagnosis

Table 8: PMD / PD

Response/Site	FDG PET-CT-Based (Complete Metabolic Response)	CT-Based (CR) ^a All of the following:

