Individual target nodes/nodal masses Extranodal lesions	Score 4 or 5 with an increase in intensity of uptake from baseline and/or new FDG-avid foci consistent with lymphoma at interim or end-of-treatment assessment	An individual node/lesion must be abnormal with: LDi > 1.5 cm & Increase by ≥ 50% from PPD nadir & An increase in LDi or SDi from nadir 0.5 cm for lesions ≤ 2cm 1.0 cm for lesions > 2cm In the setting of splenomegaly, the splenic length must increase by > 50% of the extent of its prior increase beyond baseline (eg, a 15cm spleen must increase to 16cm). If no prior splenomegaly, must increase by at least 2cm from baseline. New or recurrent splenomegaly
Non-measured lesion	None	New or clear progression of preexisting nonmeasured lesions
New lesions	New FDG-avid foci consistent with lymphoma rather than another etiology (e.g., infection, inflammation). If uncertain regarding etiology of new lesions, biopsy or interval scan may be considered.	Regrowth of previously resolved lesions A new node > 1.5cm in any axis A new extranodal site > 1.0cm in any axis; if < 1.0 cm in any axis, its presence must be unequivocal and must be attributable to lymphoma. Assessable disease of any size unequivocally attributable to lymphoma.
Bone marrow ^b	New or recurrent FDG-avid foci	New or recurrent involvement

^a CT-Based could also apply to MRI-based

^b Only if bone marrow involvement at diagnosis

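### Tables 6 to 8 of Section 9.2 carry Table 5's complete-response headings, so CT/MRI progression in Stratum 2, read as printed, needs every sign at once and contradicts Table 7 and Section 13.3(a)

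*Combined protocol and SAP*

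**What the plan says.** Section 9.2 sets the Stratum 2 response criteria in four tables: Table 5 (complete), Table 6 (partial), Table 7 (stable) and Table 8 (progressive). All four have the same two column headings: "FDG PET-CT-Based (Complete Metabolic Response") for PET and "CT-Based (CR) ^a All of the following" for CT. A footnote to each table extends the CT column to MRI: "CT-Based could also apply to MRI-based".

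Under that heading, the CT column of Table 8 lists separate signs:

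- growth of a target node or lesion;
- splenic enlargement;
- non-measured lesions ("New or clear progression of preexisting nonmeasured lesions");
- new lesions;
- marrow involvement, which by footnote applies only if marrow was involved at diagnosis.

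Table 7 allows stable disease on CT only with "no criteria for Progressive Disease met", and its new-lesion row reads "New lesions None None". Tables 5 and 6 also require that there be no new lesions.

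Section 13.3(a) counts a first new lesion as a PFS event separately from progressive disease. Section 13.4 requires that each participant be given a Section 9 category. Sections 5.2 and 5.7 also turn on whether disease has progressed.

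**The concern.** Requiring every item is right for a complete response, where all evidence of disease must be gone. Over a list of progression signs it reverses the usual logic, because a participant would have to worsen in every listed way at once. The stable-disease table assumes instead that any one sign is enough to rule stable disease out. A participant with some signs but not all then falls between the two tables.

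Three things depend on this. One is the category that Section 13.4 demands. Another is PFS, which Section 13.6 estimates within each stratum and overall, and which uses progressive disease as one of its events. The third is the meaning of disease progression in Sections 5.2 and 5.7. Progression that goes unrecorded would make PFS look longer than it is.

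**Working it through.** The plan states no figure on this point, so the check compares the tables with one another and then counts patterns.

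**What each text implies about a single progression sign**

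| Place | Is one sign enough? |
|---|---|
| Table 8, CT/MRI column, as headed | No, every item is required |
| Table 8, PET column | Yes, greater uptake and new avid foci are joined by and/or |
| Table 7, CT target row | Yes, one met criterion rules out stable disease |
| Table 7, new-lesion row | Yes, any new lesion rules out stable disease |
| Section 13.3(a) | Yes for a new lesion, which is a PFS event by itself |
| Section 9.2 opening text | Silent: it points to an external lymphoma classification without saying any or all |

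Only the CT/MRI heading of Table 8 requires all signs.

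**Counting the patterns**

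Inputs are the five CT signs in Table 8: target growth (T), splenic growth (S), non-measured progression (N), new lesion (L) and marrow (M). Each is present or absent, giving 2^5 = 32 patterns, or 2^4 = 16 where the marrow row does not apply. The count uses signs, not table rows, so it does not depend on whether the spleen text has its own row.

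- Printed rule: PD if T and S and N and L and M are all present.
- Any-one rule: PD if at least one is present.
- Table 7: SD is possible only if none is present.

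| Rule | Signs | PD | SD possible | Neither |
|---|---|---|---|---|
| All, as printed | 5 | 1 | 1 | 32 − 1 − 1 = 30 |
| All, as printed | 4 | 1 | 1 | 16 − 1 − 1 = 14 |
| Any one | 5 | 31 | 1 | 0 |
| Any one | 4 | 15 | 1 | 0 |

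The table sets PD against SD only. For a lone new lesion the gap is complete: it is not PD under the printed rule, not SD under Table 7, and neither CR nor PR, because Tables 5 and 6 exclude new lesions. The patterns are not weighted by how often they occur, so 30 of 32 measures the gap in the rule and is not a share of participants.

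**Tracing the effect on each endpoint**

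- PFS: a lone new lesion is still an event through its own clause in 13.3(a). Isolated target growth, splenic growth or worsening of an existing non-measured lesion reaches PFS only as progressive disease, so these can be missed.
- Responder proportion: 13.3 defines a responder through the Better category of 9.1 and does not use Table 8. A participant with a new lesion is a non-responder under either rule.
- Rule A: it counts Stratum 1 responders only and does not use Table 8.

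**The lymphoma wording**

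In the CT column of Table 8, attribution to lymphoma is asked only of new extranodal sites under 1.0 cm and of assessable disease of any size. Larger new nodes and sites, and regrowth, carry no such condition. In the PET column it applies to new foci in both the target and new-lesion rows.

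**Secondary point: the Deauville threshold**

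Section 9.2 grades PET uptake "with a score of ≤ 3 considered to represent a CMR" and sets no baseline condition. The PET target-lesion rows of Tables 6, 7 and 8 all need a score of 4 or 5, and entry (3.1, item 2) requires active disease without any minimum uptake. Lesions that score 1 to 3 at entry and do not change, with no new foci, can therefore only be CMR on PET. Table 4 in 9.1 puts unchanged disease in the Intermediate category, and 13.3 builds the responder definition on 9.1. Nothing maps the 9.2 categories onto Better.

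**The case against.** The strongest reply is that this is an obvious carry-over. Table 8 is titled for progression yet its heading still says CR, so no assessor would treat half of that heading as a slip and the other half as a rule. Taken literally, the heading even joins spleen conditions that exclude each other, one for existing splenomegaly and one for none. Table 7 and the PET column show that any one sign was meant. This stands as an account of what was probably intended. It does not remove the defect, because nothing in 9.2 states the CT/MRI rule correctly and sites should not have to guess it. Nor does the PET column fill the gap for everyone, since Table 2 lists CT, MRI, bone scan and PET as clinically indicated and some participants may have no PET.

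A reader might also infer more than the documents support:

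- *That CT/MRI progression is in practice almost unattainable.* This follows only from strict literal use, which the surrounding text argues against.
- *That the heading inflates the response rate.* It does not, because responder status does not rest on Table 8.
- *That new lesions count only if due to lymphoma.* In the CT column the condition covers just the two cases described above.
- *That the Deauville threshold turns unchanged disease into responses.* In an assumed subgroup of four, one such participant would move the rate by 1/4 = 25 percentage points. But 13.3 with 9.1 does not count unchanged disease as a response, and the documents do not say how often lesions score 1 to 3 at entry.

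**Conclusion.** The concern holds as an internal contradiction in the Stratum 2 criteria. Read as printed, a participant assessed by CT/MRI with some but not all progression signs is neither PD nor SD, although 13.4 requires a category. What is at risk is that category, PFS events from isolated target growth, splenic growth or non-measured progression, and consistency with the progression references in 5.2 and 5.7.

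The scope is small: up to 20 of at most 45 participants, in a stratum analysed descriptively. Stratum 2 does enter the overall PFS estimate as well as its own. The number of events that might be missed cannot be calculated, because the documents do not say how many participants will be assessed without PET or how often these signs occur alone. The conclusion assumes only that the column headings are as the authors printed them. Their repetition over four separate tables, each with its own footnotes, makes a text-extraction fault unlikely. The Deauville point is a request for clarification, not an established bias.

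**What to change.** 1. Give Tables 6, 7 and 8 their own column headings: PMR/PR, NMR/SD and PMD/PD.
2. For endpoint classification, replace the all-items wording over the CT column of Table 8 with wording that any one listed sign is enough, in line with Table 7, the PET column and 13.3(a).
3. Replace the lymphoma wording in Table 8 and in the Deauville note with the histiocytic disorder under study.
4. Have the sponsor reconcile the references to disease progression in 5.2 and 5.7 with the corrected table. No treatment rule is proposed here.
5. Clarify how the 9.2 categories map onto the responder definition in 13.3 and 9.1, including a Deauville score of 3 or less that is unchanged from baseline.

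The cost is a wording amendment to the tables and a few sentences. It needs no extra scans and no change to the sample size or to Rule A.

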⁶ End of treatment disease assessment imaging window +/- 14 days from day 28 of Cycle 6.

⁷ All Follow-Up Assessments to be performed 12, 24, and 36 months from the off-treatment date (i.e. Day 28 of last administered cycle) +/- 31 days.

⁸ 12, 24, and 36 months after completion of therapy (i.e. Day 28 of last administered cycle)

CONFIDENTIAL

This document is confidential. Do not disclose or use except as authorized.

9 CRITERIA FOR RESPONSE – STRATUM 1

In contrast to leukemia or other malignancies the terms “remission” or “relapse” should be avoided. In accordance with the nature of Histiocytosis the following definitions should be applied to judge the effect of treatment. The response criteria stated below has been designed by the Histiocyte Society to be applied in therapeutic studies of LCH and should be used for therapeutic decisions.⁶⁸

Table 3: Definition of Disease State

Main Category	Sub-categories	Definition
Non-active Disease (NAD)		Resolution of all signs/symptoms (no evidence of disease)
Active Disease (AD)	Regressive Disease (Better)	Regression of signs/symptoms, and no new lesions.
	Stable Disease (Stable)	Persistence of signs or symptoms, and no new lesions.
	Progressive Disease* (Worse)	Progression of signs/symptoms and/or appearance of new lesions.

* Progression of skeletal lesions is defined as unequivocal enlargement of the size of existing lesions and/or appearance of new lesions.

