13.6 Statistical Methods to Address Objectives

Objective 1.3 - Monitoring Rule A will be used to address primary objective 1.3. The analysis will include all evaluable Stratum 1 participants. In addition, a 95% confidence interval will be placed on the response rate.

Secondary Objective 1.4.a – Descriptive analyses using the methods of Kaplan and Meier (with standard errors per Peto) will be performed to calculate the PFS and OS within each stratum and overall. Lifetables will also be constructed.

Secondary Objective 1.4.b – Monitoring Rule B will be used to address secondary objectives 1.4.b and 1.4.c. In addition, a descriptive tabulation of the proportion of participants reporting grade 3 and higher toxicity, separately by stratum (1 and 2) and by CTC toxicity code, will be generated for all evaluable patients. A given participant will be counted only one time per toxicity code at the maximum grade regardless of the number of times that participant experienced the toxicity.

Secondary Objective 1.4.c – Within Stratum 2 and within subgroups of Stratum 2, we will calculate the proportion of evaluable patients who are responders, and place 95% confidence intervals on these proportions. A descriptive tabulation of the proportion of participants reporting grade 3 and higher toxicity, by CTC toxicity code, will be generated for Stratum 2 patients. A given participant will be counted only one time per toxicity code at the maximum grade regardless of the number of times that participant experienced the toxicity.

CONFIDENTIAL

This document is confidential. Do not disclose or use except as authorized.

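### In Stratum 2, a PET-only return of disease at an original non-marrow site after response, at or below baseline uptake, is not a PFS event

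*Combined protocol and SAP*

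**What the plan says.** Section 9.2 gives Stratum 2 a PET-based and a CT-based set of response criteria, adapted from a lymphoma classification. In Table 8 the PET entry for nodes and extranodal lesions reads "Score 4 or 5 with an increase in intensity of uptake from baseline and/or new FDG-avid foci consistent with lymphoma at interim or end-of-treatment assessment".

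Other entries in the same table treat recurrence differently:

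- The CT column measures nodes and lesions from their nadir and lists "Regrowth of previously resolved lesions" as progression.
- The PET marrow row lists "New or recurrent FDG-avid foci". It applies only where marrow was involved at diagnosis.
- The PET new-lesion row has no time limit, but it again refers to lymphoma. So does the Deauville key, which has "X = new areas of uptake unlikely to be related to lymphoma".

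The text of section 9.2 adds that metabolic progression includes radiological progression. Section 13.3 makes a PFS event the earliest of a new lesion, progressive disease or death. Section 13.6 uses Kaplan-Meier methods "to calculate the PFS and OS within each stratum and overall". Table 2 schedules disease assessments at 12, 24 and 36 months after treatment and leaves the type of imaging to clinical need.

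**The concern.** PFS ought to capture disease that responds and then comes back where it was. For a non-marrow lesion followed by PET, the rule asks for "Score 4 or 5 with an increase in intensity of uptake from baseline" or for a new focus. A lesion that was intense at entry, fell to a complete metabolic response and later became avid again at the same site, below its starting intensity, meets neither limb. The row also names only the interim and end-of-treatment assessments, although PFS follow-up runs for three years beyond treatment.

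The setting makes the pattern plausible. Section 2.1 describes relapsing and remitting disease in many patients with Rosai-Dorfman disease, one of the Stratum 2 diagnoses. A recurrence that passes uncounted, or is dated later than it occurred, makes PFS look longer. Because imaging is not fixed, the same recurrence may count in one participant and not in another, depending on which scan shows it.

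**Working it through.** The plan states no event count, sample-size basis or power for Stratum 2 PFS, so there is no figure to reproduce. The check sets the rules side by side and then applies them to an example.

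**Which rule catches a same-site return after response?**

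| Finding | Rule | PFS event? |
|---|---|---|
| New lesion at a new site | 13.3 lists new lesions separately, without lymphoma wording | Yes |
| Regrowth on CT or MRI | Table 8 CT column; 9.2 counts radiological progression | Yes |
| Recurrent marrow focus (marrow involved at diagnosis) | Table 8 PET marrow row | Yes |
| Same non-marrow site, PET only, uptake above baseline | Table 8 PET target row | Yes at interim or end of treatment; follow-up is not named |
| Same non-marrow site, PET only, uptake at or below baseline | None | No |

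Only the last row is a clear gap. Below baseline and with a residual mass, such a lesion even fits the Table 6 wording for partial metabolic response. At baseline intensity it resembles the Table 7 no-response category.

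**Example.** The uptake values are assumed: liver 3, baseline 12, lowest value 2 (complete metabolic response). Any later value above liver is taken as score 4 or 5. Rise from nadir = later value / 2 − 1.

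| Later uptake, same site | Above baseline of 12? | Progression under the PET target row | Rise from nadir |
|---|---|---|---|
| 5 | No | No | 5/2 − 1 = 150% |
| 11 | No | No | 11/2 − 1 = 450% |
| 12 | No | No | 12/2 − 1 = 500% |
| 13 | Yes | Yes | 13/2 − 1 = 550% |

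A sixfold rise from the nadir (2 to 12) is still not progression under this row.

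**Size per missed event.** Ignoring censoring, one missed event changes the event-free proportion by 1/n. Section 13.2 allows up to 20 participants in Stratum 2 and 45 in total, and expects fewer in Stratum 2.

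- n = 20: 1/20 = 5 points; two missed, 10 points; four missed, 20 points.
- n = 10 (an assumed smaller stratum): 1/10 = 10 points.
- Overall, n = 45: 1/45 = 2.2 points.

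The documents give no basis for estimating how many PET-only recurrences of this kind would occur.

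**The case against.** The strongest reply is that most recurrences are already caught. New lesions are a PFS event in their own right, regrowth on CT or MRI counts, and recurrent marrow foci count where marrow was involved at diagnosis. This stands, and it confines the point to PET-only return at an original non-marrow site.

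Three broader readings are tempting, and the documents do not support them:

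- *The lymphoma wording removes histiocytic recurrences from PFS.* Section 13.3 counts new lesions without that wording. Histiocytic sarcoma can accompany follicular lymphoma (section 2.1), but exclusion 7 in section 3.2 largely keeps out anyone with another active malignancy. The word is best read as carried over from the source classification. It leaves 9.2 and 13.3 inconsistent and should be clarified, but no bias from it alone is shown.
- *PET progression stops at end of treatment, while CT always uses the nadir.* The time limit is in the target-lesion row only, and may attach only to its new-focus limb. One CT spleen rule uses baseline.
- *Stratum 1 has the same defect.* Table 3 defines progression there as "Progression of signs/symptoms and/or appearance of new lesions". That names no reference point, so it does not exclude return after resolution. The mention of reactivation in section 3.1, "histological confirmation of reactivation or progression is not required", concerns biopsy at entry, not PFS. This is at most an ambiguity.

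It is also fair to say that Stratum 2 is exploratory, that secondary objective 1.4.a names PFS for LCH only, and that Stratum 2 PFS is descriptive. That limits the weight of the point. It does not remove it, because section 13.6 commits to the Stratum 2 and overall estimates.

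**Conclusion.** The point holds in a narrow form. After a metabolic response in Stratum 2, disease that returns on PET at an original non-marrow site, at or below baseline uptake and without CT or MRI regrowth, is not a PFS event under the rules as written. The same table treats regrowth on CT and recurrent marrow foci as progression, so the omission does not look intended.

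The effect runs in one direction: the descriptive Stratum 2 and overall PFS can come out too favourable and can vary with the scan used. The size is about 1/n per missed event (5 points at n = 20), assuming no censoring and that the participant is otherwise counted as event-free. The total is unknown, because the number of such recurrences is unknown. The uptake example shows how the rule works and is not evidence of frequency.

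Neither Rule A nor the End of Cycle 2 response endpoint depends on this. It should be corrected, but it does not threaten the trial's main conclusion.

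**What to change.** Limit the change to the PFS definition in section 13.3. Suggested content:

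*For Stratum 2, a PFS event also includes the return of FDG-avid disease (score 4 or 5) at a previously involved site after complete metabolic response, and regrowth on CT or MRI, at any assessment including the 12, 24 and 36 month follow-up. References to lymphoma in section 9.2 are read as the participant's histiocytic disorder.*

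Table 8 should not simply have its baseline comparison replaced by a nadir comparison without a threshold. Any trivial rise in a score 4 lesion would then be progression, and sections 5, 5.2 and 5.7 tie progression to continuing or stopping treatment. Whether the wording used for treatment decisions needs a matching change is for the sponsor to reconcile. A rise after only a partial metabolic response would need a defined threshold, which the documents do not give; the sponsor should state how PFS handles it.

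The cost is a short amendment. No extra scans or participants are needed. PFS may come out slightly lower.
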